# 4.2 Overall Study Design and Plan Part B

Part B is an open-label study of rilzabrutinib in patients with ITP who have relapsed or have an insufficient response to prior therapies. Eligible patients will have a platelet count  $<30,000/\mu$ L on two occasions no less than 7 days apart, within 15 days before treatment begins, and a platelet count of  $\le 35,000/\mu$ L on Study Day 1 (SD1).

The study consists of a 28-day screening period, 24-week active treatment period, and a long-term extension. After the last dose of rilzabrutinib there will be a 4-week safety follow-up period. Patients enrolled with a negative hepatitis B virus (HBV) DNA result and hepatitis B virus surface antibody (HBsAb) titer ≥100 IU/L will continue to have HBV DNA monitored monthly for 6 months after treatment has ended.

Patients will have weekly study visits/laboratory tests throughout the Part B of the study (Schedule of Assessments, Appendix 4).

# Long Term Extension (LTE)

After completing the active treatment period, patients who respond to rilzabrutinib will be allowed to enter the LTE. A platelet response is defined as platelet count  $\geq 50,000/\mu L$ , or  $\geq 30,000/\mu L$  and doubling of baseline at  $\geq 50\%$  of the visits during the last 8 weeks of the active treatment period (a minimum of 4 visits per the Schedule of Assessments) will be required. Baseline should be calculated as an average of platelet counts used for enrollment per Inclusion Criterion #4.

A patient may continue in the LTE until:

a) The patient is no longer responding as described in the table below:

[figure not shown]
Time in the LTE	'No response' platelet counts defined as <30,000/μL or <20,000/μL above baseline based on:		
C1_LTE through C6_LTE	4 consecutive weekly visits		
C7_LTE through C12_LTE	2 consecutive monthly visits		
QX_LTE	I quarterly visit  In this case, a second platelet count has to be obtained in one month to confirm lack of response		

In the LTE, patients will be monitored weekly for the first 6 months, monthly for an additional 6 months, then once every 3 months with the assessments as outlined in the LTE Schedule of Assessments Appendix 5 and Appendix 6.

# 4.3 Dose-Limiting Toxicity (DLT) Part A Only

# Hematologic:

# Non-Hematologic:

Any  $\geq$  Grade 3 non-hematologic toxicity per the CTCAE, version 4.0 will be considered a DLT, with the following exceptions:

- Laboratory TEAEs that are asymptomatic and return to baseline or to Grade 1 within 7 days
- Fatigue

- 15 May 2024 Version number: 1
- Nausea, vomiting or diarrhea that return to baseline or Grade 1 within 7 days
- Systemic reactions (such as fever, headache) that return to baseline or Grade 1 within 7 days.

### Miscellaneous:

Any toxicity that, at the discretion of the Investigator, is thought to warrant withholding the study drug for more than 7 days.

For laboratory-based AEs, these must be confirmed by repeat testing.

The DLT evaluation period for any patient is defined as the duration of rilzabrutinib dosing until the dose escalation is completed.

# 4.4 Dose Escalation Rules Part A Only

### Individual:

- Patients will dose-escalate to successive dose levels unless they are withdrawn, have a platelet response at the current dose level, or the next dose level has been determined to be ineligible for further enrollment (see Maximal Administered Dose [MAD], below)
- Patients experiencing a platelet response (as defined for the primary endpoint) will not have their dose escalated at the next cycle. If they do not experience a platelet response during the second cycle of the same dose level they may dose escalate for the following cycle. If they require rescue medication subsequently because the platelet response was only transient, these patients will be discontinued from the study.

# Starting Dose Level:

Further dose-escalation of cohort starting doses will not occur if:

- A DLT occurs in two or more patients in a sentinel cohort at the current starting dose level or the dosing level above
- A sustained platelet response (3 of 4 counts) occurs in two or more patients in a sentinel cohort at the current starting dose level
- The SMC feels that the number and/or severity of TEAEs or laboratory abnormalities occurring do not justify further dose-escalation
- Previously unknown data becomes available to the SMC which raise significant concerns about the potential risk to patients from further dose-escalation.

# Maximal Administered Dose (MAD) Level:

If any dose level is suspended for safety reasons, that dose level will be considered the MAD, and any continuing patients at the MAD will be de-escalated to the dose level below. Further enrollment will proceed at dosing levels below the MAD. If the MAD is 200 mg QD, the study will be suspended.

# 4.5 Stopping Rules Part A (also applies to LTE)

# 4.5.1 Individual Stopping Rules

- Patients experiencing a DLT will be discontinued from the study.
- Patients requiring rescue therapy during study treatment will be discontinued from the study.

15 May 2024

Version number: 1

• Pregnancy.

• Any other situation which, in the opinion of the Investigator or Sponsor, continued study treatment may result in undue safety risk to the patient.

# 4.5.2 Study Stopping Rules

The study will be stopped (no new enrollments and no further study drug administered) if:

- The MAD is determined to be 200 mg QD
- The SMC deems the emerging TEAE profile unacceptable to continue the study
- The Sponsor elects to stop the study
- There is >1 patient with Grade 3 or higher TEAEs (except for platelet count and underlying disease or comorbidity-related events)

# 4.6 Stopping Rules Part B (also applies to LTE)

# 4.6.1 Individual Stopping Rules

• Pregnancy.

• Any other situation which, in the opinion of the Investigator or Sponsor, continued study treatment may result in undue safety risk to the patient.

# 4.6.2 Study Stopping Rules

The study will be stopped (no new enrollments and no further study drug administered) if:

- The Sponsor deems the emerging TEAE profile unacceptable to continue the study
- The Sponsor elects to stop the study
- Two or more life-threatening or CTCAE Grade 4 rilzabrutinib-related TEAEs except for AEs related to the disease under study (lack of efficacy).

15 May 2024

Version number: 1

# 4.7 Number of Patients

### Part A:

Approximately 60 patients with ITP will be enrolled such that approximately 15 patients complete 24 weeks of dosing and at least 10 patients complete 24 weeks of treatment at a starting dose of 400 mg BID. Patients who drop out for reasons other than TEAEs during the 24-week treatment period may be replaced.

# Part B:

The study will enroll approximately 23 patients.

# 4.8 Study Duration and Duration of Patient Participation

# Part A:

Patients will receive rilzabrutinib treatment for 24 weeks, starting on Day 1 and ending on Study Day 169, followed by 4 weeks of post-treatment safety follow-up. The expected study duration is approximately 18 months from the first patient treated to the last patient completing, and approximately 32 weeks per patient.

Patients who are dose escalated to 400 mg BID will continue in the active treatment period until 24 weeks of treatment at the 400 mg BID dose is completed.

### Part B:

After a screening period of up to 4 weeks, patients will receive rilzabrutinib treatment for up to 24 weeks, starting on Study Day 1. All patients will complete 4 weeks of post-treatment safety follow-up.

The expected study duration is approximately 28 months from the first patient treated to last patient completing. Study duration for individual patient is approximately 32 weeks.

The duration of the LTE will be determined by the rules outlined in Section 4.6.

# 4.9 End of Study Definition (Part A and Part B)

The end of the study is defined as the date of the final safety follow-up visit after the last patient's last visit (LPLV).

15 May 2024

Version number: 1

# 4.10 Rilzabrutinib Administration (Part A and Part B)

### **4.11 Treatment of Overdose**

An overdose (accidental or intentional) with the IMP is an event suspected by the Investigator or spontaneously notified by the participant and defined as a single ingestion of a dose equal to or greater than 1200 mg (≥3 times the indicated single dose of 400 mg) provided that it has been taken at once or over a 2-hour period. No specific information is available on the treatment of overdose of rilzabrutinib.

In the event of an overdose, the Investigator should:

- Closely monitor the participant for any AE/SAE and laboratory abnormalities until rilzabrutinib can no longer be detected systemically (at least 20 hours).
- Evaluate the participant to determine, if possible, whether study intervention should be interrupted or whether the dose should be reduced.
- Obtain a plasma sample for PK analysis within 20 hours from the date of the last dose of study intervention if possible.
- Document appropriately in the eCRF.

### 4.12 Concomitant Medications

### 4.12.1 Allowed Part A

- All patients may receive, but are not required to be taking, concomitant corticosteroids. The dose should be fixed (±10%) for at least 2 weeks before Day 1 and remain unchanged throughout the study unless rescue criteria are triggered. If the patient requires rescue treatment or concomitant ITP drug increases of more than 10% of the Day 1 daily dose, the patient will be discontinued from the study and receive rescue treatment per standard of care. These drugs may not have their dose increased as part of "rescue" medication.
- Patients who continue in the LTE period will be able to taper corticosteroid dose if platelet counts are ≥100,000/μL. Tapering would follow the following guidelines with 2 weekly platelet counts between tapers:
  - 10 mg/day every one to two weeks from an initial dose >40 mg of prednisone or equivalent per day

- 15 May 2024 Version number: 1
- 5 mg/day every one to two weeks at prednisone doses ≤40 to >20 mg or equivalent per day
- 2.5 mg/day every one to two weeks at prednisone doses ≤20 to >10 mg or equivalent per day
- 1 mg/day every one to two weeks at prednisone doses ≤10 to >5 mg or equivalent per day
- 0.5 mg/day every one to two weeks at prednisone doses ≤5 mg or equivalent per day down to zero. This can be achieved by alternating daily doses (eg, 5 mg on Day one and 4 mg on day two).

Dose of corticosteroid can be up titrated if platelet counts fall below  $50,000/\mu L$  on two consecutive measurements.

• All patients may receive, but are not required to be taking, eltrombopag or romiplostim. The dose should be fixed for at least 2 weeks before Day 1 and remain constant (10% variation from Day 1 daily dose is allowed) throughout the study unless there are safety concerns related to those drugs. These drugs may not have their dose increased as part of "rescue" medication.

### 4.12.2 Allowed Part B

- All patients may receive, but are not required to be taking, concomitant corticosteroids. The dose should be fixed (±10%) for at least 2 weeks before Day 1 and remain unchanged throughout the active treatment period of the study unless rescue criteria are triggered or patient experiences corticosteroid-associated adverse events that require a reduction of steroid dose. Patients who continue in the LTE period will be able to taper corticosteroid dose if platelet counts are ≥100,000/μL. Tapering would follow the following guidelines with 2 weekly platelet counts between tapers:
  - 10 mg/day every one to two weeks from an initial dose >40 mg of prednisone or equivalent per day
  - 5 mg/day every one to two weeks at prednisone doses ≤40 to >20 mg or equivalent per day
  - 2.5 mg/day every one to two weeks at prednisone doses ≤20 to >10 mg or equivalent per day
  - 1 mg/day every one to two weeks at prednisone doses ≤10 to >5 mg or equivalent per day

- 0.5 mg/day every one to two weeks at prednisone doses ≤5 mg or equivalent per day down to zero. This can be achieved by alternating daily doses (eg, 5 mg on Day one and 4 mg on day two)
  - Dose of corticosteroid can be up-titrated if platelet counts fall below  $50,000/\mu L$  on two consecutive measurements
- All patients may receive, but are not required to be taking, eltrombopag, romiplostim, or avatrombopag. The dose should be fixed for at least 2 weeks before Day 1 and remain constant (10% variation from Day 1 daily dose is allowed) throughout the study unless there are safety concerns related to those drugs.
- Patients may receive another treatment for ITP (one form of IVIg, high-dose steroids, platelet infusion, or anti-D immunoglobulin infusion) if there is a significant safety event requiring "rescue" from a deterioration in the patient's platelet count that in the opinion of the Investigator puts the patient at significant risk of a safety event. Patients who receive rescue therapy will be allowed to continue if none of the stopping rules apply (Section 4.6) and the Investigator agrees to continue treating the patient with rilzabrutinib.

•					

### 4.12.3 Prohibited

- Concomitant use of any *immunosuppressant medication*, other than corticosteroids, as described in this protocol. Participants who need other immunosuppressant therapy during the study must be withdrawn. See Exclusion Criterion #7 in Section 6.1.2 and Section 6.2.2 for washout periods.
- Rituximab or other anti-CD20 medications, vincristine or other immunosuppressants, and new starts or increases in doses of eltrombopag, romiplostim, or avatrombopag are not permitted as rescue therapy while the patient is receiving treatment with rilzabrutinib.
- Live vaccines are not permitted during the study. See Section 6.1.2 and Section 6.2.2 for Exclusion Criterion # 20.

# 5 PROTOCOL DEVIATIONS

The Principal Investigator is responsible for complying with all protocol requirements, and applicable global and local laws regarding protocol deviations. Principia does not allow intentional or prospective deviations from the protocol unless necessary to eliminate an immediate hazard to study patients. The Principal Investigator is responsible for immediately (within 24 hours) notifying the CRO of a major protocol deviation to permit Principia to determine the impact of the deviation on the patient and/or the study.

15 May 2024

Version number: 1

The Principal Investigator is responsible for notifying Independent Ethics Committee (IEC)/Independent Review Board (IRB) regulatory authorities. The contract research organization (CRO) Clinical Monitors will notify the Sponsor.

# **6 STUDY POPULATION**

# 6.1 Part A

# 6.1.1 Inclusion Criteria

1. Male and female patients, aged 18 to 80 years old (Czech Republic and Norway only: aged 18 to 65 years old)

15 May 2024

[figure not shown]
Version number: 1

- 2. Immune-related ITP (both primary and secondary)
- 3. Refractory or relapsed patients with no available and approved therapeutic options with a platelet count of count <30,000/μL on two occasions no less than 7 days apart in the 15 days prior to beginning study treatment
- 4. A history of response (two or more platelet counts ≥50,000/μL with an increase of ≥20,000/μL) to at least one prior line of therapy (with splenectomy being considered a line of therapy)
- 5. Adequate hematologic, hepatic, and renal function (absolute neutrophil count ≥1.5 × 10^9/L, hemoglobin [Hgb] >9 g/dL, AST/ALT ≤1.5 × ULN, albumin ≥3 g/dL, total bilirubin ≤1.5 × ULN, estimated glomerular filtration rate [eGFR] >60 mL/min (Cockcroft and Gault method) (C1D1 pre-dose may be checked up to Day 3 prior to C1D1)
- 6. Female patients who are of reproductive potential must agree for the duration of active treatment in the study to use a highly effective means of contraception (hormonal contraception methods that inhibits ovulation, intrauterine device, intrauterine hormonereleasing system, bilateral tubal ligation, vasectomized partner, or true abstinence: when this is in line with the preferred and usual lifestyle of the patient). Unless surgically sterile, postmenopausal females should have menopause confirmed by follicle-stimulating hormone (FSH) testing.
- 7. Able to provide written informed consent and agreeable to the schedule of assessments.

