### 6.2 Part B

### 6.2.1 Inclusion Criteria

- 1. Male or female patients, aged 18 to 80 years old
- 2. Patients with immune-related ITP (both primary and secondary) as defined by current guidelines with at least 3 months duration
- 3. Patients who had a response (achievement of platelet count ≥50,000/µL) to IVIg/anti-D or corticosteroid that was not sustained and failed at least one other ITP therapy (that was not IVIg or corticosteroid)
- 4. Patients with a platelet count of  $<30,000/\mu L$  on two occasions no less than 7 days apart in the 15 days before treatment begins, and no platelet count above  $35,000/\mu L$  on Study Day 1.
- 5. Patients with adequate hematologic, hepatic, and renal function (absolute neutrophil count ≥1.5 × 10^9/L, Hgb >9 g/dL, AST/ALT ≤1.5 × ULN, albumin ≥3 g/dL, total bilirubin ≤1.5 × ULN, eGFR >50 mL/min (Cockcroft and Gault method) (pre-dose may be checked up to Day -3)
- 6. Female patients who are of reproductive potential must agree for the duration of active treatment in the study to use a highly effective means of contraception (hormonal contraception methods that inhibits ovulation, intrauterine device, intrauterine hormonereleasing system, bilateral tubal ligation, vasectomized partner, or true abstinence; when this is in line with the preferred and usual lifestyle of the patient). Unless surgically sterile, postmenopausal females should have menopause confirmed by FSH testing.
- 7. Able to provide written informed consent and agreeable to the schedule of assessments.

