3.4.5 Baseline for Platelet Count

The average of the 2 screening results and the Cycle 1 Day 1 result will be used as the Baseline value for platelet count. If at least one of the platelet counts is missing, the average of the non-missing platelet counts will be used. This baseline value will be used for the main treatment period and LTE period analyses.

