5.4.1 Primary Efficacy Endpoint

Platelet count is measured at visits as specified in the Schedule of Assessments (Table 3 to Table 6).

The primary efficacy endpoint is:

 Proportion of patients able to achieve two or more consecutive platelet counts, separated by at least 5 days, of ≥ 50,000/µL AND an increase of platelet count of ≥ 20,000/µL from baseline, by dose level, without use of rescue medication in the 4 weeks prior to the latest elevated platelet count.

The number and percentage of patients who meet the primary efficacy endpoint criteria in the main treatment period will be tabulated by dose level and overall. A 95% confidence interval will be calculated for the proportions using the Clopper-Pearson method. The response will be attributed to the dose level at the visit prior to the first of the two consecutive scheduled platelet counts occurred that are at least 5 days apart, see table below. A patient can have multiple responses within the same dose level and/or at different dose levels. This table will be repeated by starting dose.

Example 1: Patient had a response at 200 dose only			Example 2: Patient had a response at 200 and 400 doses.						
Visit	Dose	Platelets	Response	Dose that	Visit	Dose	Platelets	Response	Dose that
	dispensed			response is		dispensed			response is
	at this visit			attributed to		at this visit			attributed to
C1D1	200	25			C1D1	200	25		
C1D8	200	30		200	C1D8	200	30		200
C1D15	200	35		200	C1D15	200	35		200
C2D1	400	51	Υ	200	C2D1	400	51	Υ	200
C2D8	400	55		400	C2D8	400	55	Y	400
C2D15	400	42		400	C2D15	400	53		400
C3D1	600	39		400	C3D1	600	39		400
C3D8	600	40		600	C3D8	600	40		600
C3D15	600	41		600	C3D15	600	41		600
Example 3: Patient had a response at 200 and 600 doses.			Example 4: Patient had a response at 200, 400 and 600 doses.						
Visit	Dose	Platelets	Response	Dose that	Visit	Dose	Platelets	Response	Dose that
	dispensed			response is		dispensed			response is
	at this visit			attributed to		at this visit			attributed to
C1D1	200	25			C1D1	200	25		
C1D8	200	30		200	C1D8	200	30		200
C1D15	200	35		200	C1D15	200	35		200
C2D1	400	51	Υ	200	C2D1	400	51	Υ	200
C2D8	400	55		400	C2D8	400	55	Υ	400
C2D15	400	42		400	C2D15	400	53		400
C3D1	600	43		400	C3D1	600	39		400
C3D8	600	59	Υ	600	C3D8	600	59	Υ	600
C3D15	600	59		600	C3D15	600	59		600

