5.4.2.4 Number of weeks with platelet counts \geq 50,000/ μ L across all dose levels

The number of weeks that patients achieved platelet counts $\geq 50,000/\mu L$ in the main treatment period will be summarized across all dose levels. Summaries will be repeated in these 2 groups of patients: those that intended to finish the study drug at 12 weeks, i.e., patients who enrolled under protocol version v7.0and those that intended to finish at 24 weeks, i.e., patients who enrolled under protocol version 8.0 and up. This table will be repeated by Starting Dose.

5.4.2.5 Number of weeks with platelet counts \geq 30,000/ μ L across all dose levels

The number of weeks that patients achieved platelet counts \geq 30,000/ μ L in the main treatment period will be summarized across all dose levels. Summaries will be repeated in these 2 groups of patients: those that intended to finish the study drug at 12 weeks, i.e., patients who enrolled under protocol version v7.0 and those that intended to finish at 24 weeks i.e., patients who enrolled under protocol version 8.0 and up. This table will be repeated by Starting Dose.

5.4.2.6 Time to first platelet count \geq 50,000/ μ L across all dose levels

Time to first platelet count ≥ 50,000/μL during the main treatment period in days will be calculated as:

(Date of first occurrence of platelet count ≥ 50,000/μL – Date of first study drug dosing) +1

[figure not shown]
Patients who did not experiencing platelet count ≥ 50,000/µL will be censored

[figure not shown]
- at the end of the main on-treatment period for those who completed the main treatment period,
- at Week 25 (ie, 1 week after the protocol scheduled Week 24 visit) for those who prematurely discontinued the main treatment due to any AE or lack of response, and
- at the time of discontinuation for those who prematurely discontinued the main treatment due to other reasons.

[figure not shown]
All platelet counts including unscheduled measurements will be included. The number of days to first platelet count $\geq 50,000/\mu$ L will be summarized by descriptive statistics for overall across all dose levels.

Kaplan-Meier estimates will be calculated for time to first platelet \geq 50,000/ μ L. The 25%, median and 75% time to event will be produced with the corresponding 2-sided 95% confidence intervals. Kaplan-Meier plot will also be provided.

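### Part A sets no limit on the pre-dose Day 1 platelet count, and the averaged baseline gives that count only one-third weight, so a patient whose count rose before the first dose can be a primary-endpoint responder with no rise on drug

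*Protocol*

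**What the plan says.** **Entry, Part A.** Protocol 6.1.1 criterion 3 asks for a count below 30,000/µL "on two occasions no less than 7 days apart in the 15 days prior to beginning study treatment". No visible Part A text limits the C1D1 count. Appendix 3 repeats the eligibility check at C1D1, but two earlier low counts satisfy criterion 3 whatever C1D1 shows.

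**Entry, Part B.** Protocol 6.2.1 criterion 4 has the same two-count rule "in the 15 days before treatment begins, and no platelet count above" 35,000/µL on Study Day 1.

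**Baseline, Part A.** SAP 3.4.5: "The average of the 2 screening results and the Cycle 1 Day 1 result will be used as the Baseline value for platelet count". The footnotes to the schedules in SAP 2.7 say that Day 1 assessments are done before dosing.

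**Primary endpoint, Part A.** SAP 5.4.1: "Proportion of patients able to achieve two or more consecutive platelet counts, separated by at least 5 days, of" at least 50,000/µL, with a rise of at least 20,000/µL from baseline, "without use of rescue medication in the 4 weeks prior to the latest elevated platelet count". On dose attribution: "The response will be attributed to the dose level at the visit prior to the first of the two consecutive scheduled platelet counts occurred".

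**Time to first count of at least 50,000/µL.** SAP 5.4.2.6 counts days from first dosing, with the dosing date as Day 1, and adds: "All platelet counts including unscheduled measurements will be included".

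**Baseline subsets.** SAP 5.4.1.1, item 8, has two strata, up to 15,000/µL and above 15,000 to 30,000/µL.

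**The concern.** Part A is a single-arm, open-label, dose-finding study that selects patients on two low counts. Some of them will drift upward before the first dose through ordinary fluctuation or regression to the mean. The endpoint's second limb, the 20,000/µL rise, is what should separate a change on drug from a count that was already high. It is measured from an average in which two of the three values are required to be low, so it can be met by a rise that happened between screening and C1D1. That response is then credited to the starting dose. There is no control arm to offset it, and the Part A SAP has no exclusion, flag or sensitivity analysis for it. Protocol 4.4 also uses the primary-endpoint response to decide whether a patient escalates at the next cycle, so the definition matters beyond the summary table.

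**Working it through.** **The plan's own figure (context only).** Protocol 10.5 assumes a 40% response in 15 evaluable patients. The two-sided 80% normal half-width is 1.28 × √(0.40 × 0.60 / 15) = 0.162, so the lower limit is 0.238. This reproduces the stated ±16% and 24%. The plan gives no figure for the present point.

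**Inputs.** Let a be the mean of the two screening counts (below 30), c the C1D1 pre-dose count, and y each on-drug count, all in thousands/µL. Baseline b = (2a + c)/3 (SAP 3.4.5). A response needs two qualifying counts with y ≥ 50 and y − b ≥ 20 (SAP 5.4.1). Under the attribution rule, Day 8 is the earliest count that can start an attributed response, so two on-drug counts are needed.

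**Flat patient.** Set y = c. The rise limb becomes c − (2a + c)/3 = 2(c − a)/3 ≥ 20, that is c ≥ a + 30. With the first limb, the condition is c ≥ max(50, a + 30).

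| Screening mean a | Smallest flat c that responds, SAP baseline | Same, screening-only baseline |
|---|---|---|
| 20 or below | 50 | 50 |
| 25 | 55 | 50 |
| 29 | 59 | 50 |

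**Worked patients.**
- 20, 20, C1D1 50, then 50, 50: b = 30, change +20. Responder, with no rise on drug.
- 29, 29, C1D1 59, then 59, 59: b = 39, change +20. Responder.
- 29, 29, C1D1 58, then 58, 58: b = 38.7, change +19.3. Not a responder.
- 10, 10, C1D1 70, then 50, 50: b = 30, change +20. Responder, although the count fell by 20 on drug.

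**Under Part B's limit.** With c ≤ 35, reaching 50 takes a rise of at least 50 − 35 = 15 on drug, and b is below (30 + 30 + 35)/3 = 31.7. A flat patient cannot respond.

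**Measuring from max(b, c).** The threshold becomes max(50, max(b, c) + 20). If c ≤ 30, then b < 30 and the threshold is 50 under either rule, so nothing changes. The rule bites only when C1D1 exceeds 30,000/µL. The first worked patient would then need 70, and the last would need 90.

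**Size.** One patient is 1/60 = 1.7 points of the overall rate at the planned enrolment.

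**How often (illustration on assumed inputs).** The documents give no within-patient platelet variability. A simulation with no drug effect assumed a median of 18,000/µL, between-patient log-SD 0.5, within-patient log-SD 0.3 to 0.7, and week-to-week correlation 0 to 0.8. It gave:
- C1D1 of at least 50,000/µL in about 0 to 6% of eligible patients;
- responders on the first two on-drug counts with no rise over C1D1 in under 0.05%, or under 0.03 of 60 patients;
- all responders on those two counts in about 0.02 to 1.8%, of whom roughly 32 to 70% had C1D1 above 35,000/µL.

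These shares cover two counts, not the whole treatment period.

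**The case against.** The strongest reply is that the route is narrow and partly guarded. Exclusions 4 to 6 in Protocol 6.1.2 bar transfusion, changes in corticosteroid or TPO-agonist dose, and other rescue for two weeks before Day 1. The endpoint bars rescue for four weeks. The individual platelet profiles in SAP 5.4.1 would show a high C1D1 to anyone who looks, and the durability measures (4 of the final 8 counts, 8 of the final 12) are less exposed to a transient rise. All this stands and lowers the expected number. None of it deals with a spontaneous rise, and none changes how the primary endpoint scores one.

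Five stronger readings might be inferred, and the documents do not support them:
- *Averaging C1D1 into baseline is the error.* It makes the endpoint stricter than a screening-only baseline, as the table shows, and SAP Part B 4.1 uses the same three-count average.
- *One patient moves a dose-level rate by 1/15.* Fifteen is the number in the precision statement. Under SAP 5.4, a dose-level analysis takes everyone who received that dose at least once, and those numbers are not given.
- *A high C1D1 count is definitely a Day 1 event in 5.4.2.6.* SAP 3.4.1 starts the on-treatment period at the first dose but the main on-treatment period at the date of that dose, and 3.3.1 assigns time-to-event analyses by the dose received before the visit. The text is ambiguous rather than wrong.
- *Part B's limit was added to repair Part A, or the two rates are invalidly compared.* The documents state no such motive and plan no test between the parts, whose primary endpoints and other entry criteria also differ.
- *A 35,000/µL limit would remove spontaneous responders.* In the simulation, 30 to 68% of them had C1D1 at or below that value.

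**Conclusion.** The gap is real. As written, the Part A rules classify a patient as a responder when C1D1 is at least max(50,000, screening mean + 30,000)/µL and the count then stays flat. The cause is the missing Day 1 limit together with the one-third weight on the only count taken immediately before treatment. Each such patient shifts the rate upward, by 1.7 points if the denominator is 60.

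The number of such patients is not given and is probably small, so this does not show that the Part A response rate is materially inflated. That judgement of rarity rests on assumed platelet variability. The algebra rests only on the documents. One limit on the finding is that some Part A exclusion criteria are redacted in the public copy; nothing visible suggests that they contain a platelet limit.

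**What to change.** Keep the primary definition. From data already collected:
- **SAP Part A 5.4.1:** add a sensitivity analysis, by dose level and overall, that requires the 20,000/µL rise over the higher of the averaged baseline and the C1D1 pre-dose count. Excluding patients with C1D1 above 35,000/µL is a simpler alternative.
- **Listing:** list patients with C1D1 above 35,000/µL. If there are none, one sentence in the report says so.
- **SAP Part A 5.4.1.1, item 8:** add a stratum for baseline above 30,000/µL, which the averaged baseline can reach.
- **SAP Part A 5.4.2.6:** state that only counts taken after the first dose can be events.

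SAP Part B 1.1 says that the main Part A period is complete (data cutoff 04 May 2021) and that a study report has been prepared. Any analysis added now should therefore be labelled post hoc.

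The cost is one extra table, a short listing and a few lines of text. The sensitivity rate may be slightly lower than the main one. The stricter rule can also miss a genuine drug effect in a patient who starts high, which is a reason to use it as a sensitivity analysis and not as a replacement.
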